8.2.2 Reporting of Pregnancy and Lactation to the Sponsor

Although pregnancy and lactation are not considered adverse events, it is the responsibility of investigators or their designees to report any pregnancy or lactation in a subject (spontaneously reported to them), including the pregnancy of a male subject’s female partner that occurs during the trial or within 120 days of completing the trial. All subjects and female partners of male subjects who become pregnant must be followed to the completion/termination of the pregnancy. Pregnancy outcomes of spontaneous abortion, missed abortion, benign hydatidiform mole, blighted ovum, fetal death, intrauterine death, miscarriage and stillbirth must be reported as serious events (Important Medical Events). If the pregnancy continues to term, the outcome (health of infant) must also be reported.

Such events must be reported within 24 hours to the Sponsor and within 2 working days to Merck Global Safety. (Attn: Worldwide Product Safety; [contact])

8.2.3 Immediate Reporting of Adverse Events to the Sponsor

8.2.3.1 Serious Adverse Events

A serious adverse event is any adverse event occurring at any dose or during any use of Merck’s product that:

- Results in death;
- Is life threatening;
- Results in persistent or significant disability/incapacity;
- Results in or prolongs an existing inpatient hospitalization;
- Is a congenital anomaly/birth defect;
- Is a new cancer (that is not a condition of the study);
- Is associated with an overdose;
- Is another important medical event

Phase II Pembrolizumab Reirradiation

SAE reports and any other relevant safety information are to be forwarded to the Merck Global Safety [contact] within two (2) business days of learning of the information.

A copy of all 15 Day Reports and Annual Progress Reports is submitted as required by FDA, European Union (EU), Pharmaceutical and Medical Devices agency (PMDA) or other local regulators. Investigators will cross reference this submission according to local regulations to the Merck Investigational Compound Number (IND, CSA, etc.) at the time of submission. Additionally, investigators will submit a copy of these reports to Merck & Co., Inc. (Attn: Worldwide Product Safety; [contact]) at the time of submission to FDA.

All subjects with serious adverse events must be followed up for outcome.

8.2.3.2 Events of Clinical Interest

Selected non-serious and serious adverse events are also known as Events of Clinical Interest (ECI) and must be reported within 24 hours to the Sponsor and within 2 working days to Merck Global Safety. (Attn: Worldwide Product Safety; [contact]).

For the time period beginning when the consent form is signed until treatment allocation/randomization, any ECI, or follow up to an ECI, that occurs to any subject must be reported within 24 hours to the Sponsor and within 2 working days to Merck Global Safety if it causes the subject to be excluded from the trial, or is the result of a protocol-specified intervention, including but not limited to washout or discontinuation of usual therapy, diet, placebo treatment or a procedure.

For the time period beginning at treatment allocation/randomization through 90 days following cessation of treatment, or 30 days following cessation of treatment if the subject initiates new anticancer therapy, whichever is earlier, any ECI, or follow up to an ECI, whether or not related to Merck product, must be reported within 24 hours to the Sponsor and within 24 hours to Merck Global Safety.

Events of clinical interest for this trial include:

1. an overdose of Merck product, as defined in Section 7.2.1 - Definition of an Overdose for This Protocol and Reporting of Overdose to the Sponsor, that is not associated with clinical symptoms or abnormal laboratory results.
2. an elevated AST or ALT lab value that is greater than or equal to 3X the upper limit of normal and an elevated total bilirubin lab value that is greater than or equal to 2X the upper limit of normal and, at the same time, an alkaline phosphatase lab value that is less than 2X the upper limit of normal, as determined by way of protocol-specified laboratory testing or unscheduled laboratory testing.*

Note: These criteria are based upon available regulatory guidance documents. The purpose of the criteria is to specify a threshold of abnormal hepatic tests that may require an additional evaluation for an underlying etiology.

8.2.4 Evaluating Adverse Events

An investigator who is a qualified physician will evaluate all adverse events according to the NCI CTCAE, version 5.0. Any adverse event which changes CTCAE grade over the course of a given episode will have each change of grade recorded on the adverse event case report forms/worksheets. All adverse events regardless of CTCAE grade must also be evaluated for seriousness.

Table 8: Evaluating Adverse Events

An investigator who is a qualified physician, will evaluate all adverse events as to:

V5.0 CTCAE Grading	Grade 1	Mild; asymptomatic or mild symptoms; clinical or diagnostic observations only; intervention not indicated.
	Grade 2	Moderate; minimal, local or noninvasive intervention indicated; limiting age-appropriate instrumental ADL.
	Grade 3	Severe or medically significant but not immediately life-threatening; hospitalization or prolongation of hospitalization indicated; disabling; limiting self-care ADL.
	Grade 4	Life threatening consequences; urgent intervention indicated.
	Grade 5	Death related to AE
Seriousness	
A serious adverse event is any adverse event occurring at any dose or during any use of Merck product that:
 
†Results in death; or
 
†Is life threatening; or places the subject, in the view of the investigator, at immediate risk of death from the event as it occurred (Note: This does not include an adverse event that, had it occurred in a more severe form, might have caused death.); or
 
†Results in a persistent or significant disability/incapacity (substantial disruption of one's ability to conduct normal life functions); or
 
†Results in or prolongs an existing inpatient hospitalization (hospitalization is defined as an inpatient admission, regardless of length of stay, even if the hospitalization is a precautionary measure for continued observation. (Note: Hospitalization [including hospitalization for an elective procedure] for a preexisting condition which has not worsened does not constitute a serious adverse event.); or
 
†Is a congenital anomaly/birth defect (in offspring of subject taking the product regardless of time to diagnosis); or
 
Is a new cancer; (that is not a condition of the study) or
 
Is an overdose (whether accidental or intentional). Any adverse event associated with an overdose is considered a serious adverse event. An overdose that is not associated with an adverse event is considered a non-serious event of clinical interest and must be reported within 24 hours.
 
Other important medical events that may not result in death, not be life threatening, or not require hospitalization may be considered a serious adverse event when, based upon appropriate medical judgment, the event may jeopardize the subject and may require medical or surgical intervention to prevent one of the outcomes listed previously (designated above by a †).
	
Duration	
Record the start and stop dates of the adverse event. If less than 1 day, indicate the appropriate length of time and units
	
Action taken	
Did the adverse event cause the Merck product to be discontinued?
	
Relationship to test drug	
Did the Merck product cause the adverse event? The determination of the likelihood that the Merck product caused the adverse event will be provided by an investigator who is a qualified physician. The investigator's signed/dated initials on the source document or worksheet that supports the causality noted on the AE form, ensures that a medically qualified assessment of causality was done. This initialed document must be retained for the required regulatory time frame. The criteria below are
	

	
intended as reference guidelines to assist the investigator in assessing the likelihood of a relationship between the test drug and the adverse event based upon the available information.
 
The following components are to be used to assess the relationship between the Merck product and the AE; the greater the correlation with the components and their respective elements (in number and/or intensity), the more likely the Merck product caused the adverse event (AE):

	
Exposure Is there evidence that the subject was actually exposed to the Merck product such as: reliable history, acceptable compliance assessment (pill count, diary, etc.), expected pharmacologic effect, or measurement of drug/metabolite in bodily specimen?

	
Time Course Did the AE follow in a reasonable temporal sequence from administration of the Merck product? Is the time of onset of the AE compatible with a drug-induced effect (applies to trials with investigational medicinal product)?

	
Likely Cause Is the AE not reasonably explained by another etiology such as underlying disease, other drug(s)/vaccine(s), or other host or environmental factors

Relationship to Merck product (continued)	The following components are to be used to assess the relationship between the test drug and the AE: (continued)	
	
Decchallenge Was the Merck product discontinued or dose/exposure/frequency reduced? If yes, did the AE resolve or improve? If yes, this is a positive dechallenge. If no, this is a negative dechallenge. (Note: This criterion is not applicable if: (1) the AE resulted in death or permanent disability; (2) the AE resolved/improved despite continuation of the Merck product; or (3) the trial is a single-dose drug trial); or (4) Merck product(s) is/are only used one time.)
	
	
Rechallenge Was the subject re-exposed to the Merck product in this study? If yes, did the AE recur or worsen? If yes, this is a positive rechallenge. If no, this is a negative rechallenge. (Note: This criterion is not applicable if: (1) the initial AE resulted in death or permanent disability, or (2) the trial is a single-dose drug trial); or (3) Merck product(s) is/are used only one time). NOTE: IF A RECHALLENGE IS PLANNED FOR AN ADVERSE EVENT WHICH WAS SERIOUS AND WHICH MAY HAVE BEEN CAUSED BY THE MERCK PRODUCT, OR IF REEXPOSURE TO THE MERCK PRODUCT POSES ADDITIONAL POTENTIAL SIGNIFICANT RISK TO THE SUBJECT, THEN THE RECHALLENGE MUST BE APPROVED IN ADVANCE BY THE U.S. CLINICAL MONITOR AS PER DOSE MODIFICATION GUIDELINES IN THE PROTOCOL.
	
	
Consistency with Trial Treatment Profile Is the clinical/pathological presentation of the AE consistent with previous knowledge regarding the Merck product or drug class pharmacology or toxicology?
	

The assessment of relationship will be reported on the case report forms /worksheets by an investigator who is a qualified physician according to his/her best clinical judgment, including consideration of the above elements.
	
Record one of the following	Use the following scale of criteria as guidance (not all criteria must be present to be indicative of a Merck product relationship).
Yes, there is a reasonable possibility of Merck product relationship.	There is evidence of exposure to the Merck product. The temporal sequence of the AE onset relative to the administration of the Merck product is reasonable. The AE is more likely explained by the Merck product than by another cause.
No, there is not a reasonable possibility Merck product relationship	Subject did not receive the Merck product OR temporal sequence of the AE onset relative to administration of the Merck product is not reasonable OR there is another obvious cause of the AE. (Also entered for a subject with overdose without an associated AE.)

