8.2 Assessing and Recording Adverse Events

An adverse event is defined as any untoward medical occurrence in a patient or clinical investigation subject administered a pharmaceutical product and which does not necessarily have to have a causal relationship with this treatment. An adverse event can therefore be any unfavorable and unintended sign (including an abnormal laboratory finding, for example), symptom, or disease temporally associated with the use of a medicinal product or protocol-specified procedure, whether or not considered related to the medicinal product or protocol-specified procedure. Any worsening (i.e., any clinically significant adverse change in frequency and/or intensity) of a preexisting condition that is temporally associated with the use of the Merck's product, is also an adverse event.

Merck product includes any pharmaceutical product, biological product, device, diagnostic agent or protocol-specified procedure, whether investigational (including placebo or active comparator medication) or marketed, manufactured by, licensed by, provided by or distributed by Merck for human use.

Phase II Pembrolizumab Reirradiation

Adverse events may occur during the course of the use of Merck product in clinical trials or within the follow-up period specified by the protocol, or prescribed in clinical practice, from overdose (whether accidental or intentional), from abuse and from withdrawal.

All adverse events will be recorded from beginning with cycle 1 of Pembrolizumab through 30 days following cessation of treatment and at each examination on the Adverse Event case report forms/worksheets. Laboratory AE's will also start being recorded beginning with cycle 1 of Pembrolizumab. The reporting timeframe for adverse events meeting any serious criteria is described in section 8.2.3.1.

Applicable reporting to DSMC will occur as follows:

On-Site subjects (this includes any subjects enrolled at other sites on an in-house study)

1. All grade 3 or higher events (AE or SAE) within five business days of knowledge.
2. All unexpected deaths within 24 hours of knowledge.
3. All others deaths within 30 days of knowledge. Deaths of subjects off-study for greater than 30 days from the last study treatment/intervention are not reportable with the following exceptions:

Study Exceptions the CTSRMC will not Approve:

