- An event is considered a "suspected adverse reaction" when there is reasonable possibility that the drug/investigational product caused the adverse event. For these reporting purposes, reasonable possibility means there is evidence to suggest a causal relationship between the drug/investigational product and the event.
- For University of Pennsylvania IRB reporting, this means an event should be considered probably or definitely related to the research procedures.
- An event is "unexpected" if it is not listed in the investigator's brochure/package insert, or, is not listed at the specificity or severity that has previously been observed with the specific drug/investigational product; if an investigator's brochure/package insert is not available, is not consistent with the risk information described in the general investigational plan.)
- "Unexpected" also refers to events that are mentioned in the investigator's brochure/package insert as occurring with a class of drugs or as anticipated, but, are not mentioned as to have been occurring (have been seen) with the particular drug/investigational product under study.

(2) Unanticipated adverse device reaction. Any serious adverse effect on health or safety or any life-threatening problem or death caused by, or associated with, a device, if that effect, problem, or death was not previously identified in nature, severity, or degree of incidence in the investigational plan or application (including a supplementary plan or application, or any other unanticipated serious problem associated with a device that relates to the rights, safety, or welfare of subjects.

- For drug/investigational product and device events, "serious" is defined as any death, life-threatening adverse event, inpatient hospitalization or prolongation of existing hospitalization, a persistent or significant incapacity or substantial disruption of the ability to conduct normal life functions, or a congenital anomaly/birth defect. Other events that may be considered "serious" but not meet the prior criteria include: those events that may jeopardize the patient or subject and may require medical or surgical intervention to prevent one of the outcomes noted above.

(3) In addition to unanticipated problems, the IRB also requires prompt reporting of the following events:

- Complaint of a participant when the complaint indicates unexpected risks or the complaint cannot be resolved by the research team.

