9.3.1 Analysis Endpoints

Primary

Progression Free Survival (PFS) per RECIST 1.1

Progression Free Survival is defined as the time from initiation of definitive therapy to the first documented disease progression per RECIST 1.1 based on radiologists' review or death due to any cause, whichever occurs first, or last patient follow-up that documented lack of disease progression. Patients who have not had disease progression or who have died, will be censored on the most recent clinical evaluation date that documented that they were progression-free.

Secondary

Overall Survival

Overall Survival (OS) is defined as the time from initiation of definitive therapy to death due to any cause or last patient contact alive. Subjects without documented death at the time of the final analysis will be censored at the date of the last follow-up.

Toxicity Determination

Tolerability of therapy will be determined on the basis of CTCAE adverse event reporting. Toxicity will be reported separately for definitive therapy and Pembrolizumab. For the definitive therapy phase, we will report on adverse events which are grade 3 or higher treatment-related toxicities or any grade of pneumonitis or esophagitis. For the Pembrolizumab phase, we will report all treatment-related toxicities.

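### Definitive-phase toxicity is to be reported as treatment-related, but the only causality assessment the protocol describes covers the Merck product alone

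*Combined protocol and SAP*

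**What the plan says.** Toxicity is a secondary endpoint (Sections 2 and 3.3). Section 9.3.1 splits it by phase: "Toxicity will be reported separately for definitive therapy and Pembrolizumab". For definitive therapy, "we will report on adverse events which are grade 3 or higher treatment-related toxicities or any grade of pneumonitis or esophagitis"; Section 9.4 repeats the rule. For the pembrolizumab phase, all treatment-related toxicities are to be reported. Neither section says what the treatment is to which a definitive-phase event must be related.

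Causality is described in Table 8 of Section 8.2.4. Its question is "Did the Merck product cause the adverse event", and each supporting element (exposure, time course, likely cause, dechallenge, rechallenge, consistency) serves that question. The investigator records yes or no on the case report form. The negative answer is worded "No, there is not a reasonable possibility Merck product relationship". It applies where "Subject did not receive the Merck product OR temporal sequence of the AE onset relative to administration of the Merck product is not reasonable", or where the event has another obvious cause. Section 8.2 limits Merck product to items "manufactured by, licensed by, provided by or distributed by Merck for human use".

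Sections 3.1, 8.1.2.1 and 8.2 start adverse event monitoring, grading and recording with pembrolizumab. The flow chart in Section 7.1 has no adverse event review in the reirradiation column.

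**The concern.** A table of treatment-related events needs a relatedness judgement against the treatment in question, made by the investigator near the time of the event. For the definitive phase that treatment is proton reirradiation, with or without chemotherapy. The protocol describes a judgement against a different product, one that no patient has yet received on study.

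This matters because reirradiation is where Section 1.1 itself places much of the risk: it describes local retreatment in this setting as highly toxic and says toxicity has limited its use. If relatedness to reirradiation is not recorded, someone must assign it afterwards by an unstated rule, in an open-label single-arm trial, or fall back on the pembrolizumab field. Either route weakens the safety description of the phase, and the second would understate its toxicity.

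**Working it through.** No figure in the plan is in dispute. The check sets the passages side by side and uses simple arithmetic for scale.

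1. **What the analysis needs.** Sections 9.3.1 and 9.4: for each definitive-phase event of grade 3 or higher, a flag for treatment-related. Pneumonitis and esophagitis are reported at any grade and, on the wording, need no flag.

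2. **What is described as recorded.** Table 8: one yes/no answer on relationship to the Merck product. The definition in Section 8.2 gives no basis for counting proton therapy or standard chemotherapy as a Merck product. No other relationship item appears in the documents.

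3. **Event before pembrolizumab.** Non-receipt of the product leads to a negative answer. This is correct as a statement about pembrolizumab and says nothing about reirradiation. The flag in step 1 cannot be derived from it.

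4. **Event during pembrolizumab that the investigator attributes to earlier radiation.** Another obvious cause also leads to a negative answer. If treatment-related in the pembrolizumab phase is read from Table 8, the event is left out of that table. It enters the definitive-phase table only if that phase is defined to include late events and relation to radiation was noted, and neither is specified. The event can therefore be absent from both.

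5. **Whom it touches.** During definitive therapy all 41 planned patients are unexposed to on-study pembrolizumab. Section 9.4 expects up to 15% never to start it: 41 × (1 − 0.15) = 34.85, which matches the stated 35 and leaves 41 − 35 = 6 patients who would stay unexposed throughout.

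6. **Interaction with the recording window.** Section 3.1 gives about 3 to 8 weeks of radiation and then 4 to 12 weeks before pembrolizumab. The interval from first fraction to cycle 1 is therefore about 3 + 4 = 7 to 8 + 12 = 20 weeks. Sections 3.1, 8.1.2.1 and 8.2 describe no general adverse event recording in that interval. Adding attribution items without changing the window leaves no definitive-phase events to attribute. Changing the window without adding the items yields events that lack the attribution Sections 9.3.1 and 9.4 require. The window gap also reaches pneumonitis and esophagitis, which the attribution gap does not.

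**The case against.** The best reply is that Table 8 was never meant to serve the definitive-phase report. Its negative answer means not related to the Merck product, and no section says the definitive-phase flag comes from that row. Since toxicity is reported separately by phase, treatment-related in the first phase naturally means related to definitive therapy. Table 8 also presents its criteria softly ("Use the following scale of criteria as guidance") and leaves the decision to clinical judgement. The case report form is not in the documents, and Section 10.6 leaves data-management detail to the sponsor, so a suitable field may exist. Section 8.1.2.1 mentions causality without limiting it to pembrolizumab, although it does so within recording that starts at pembrolizumab.

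Much of this stands. A reader might infer that the grade 3 or higher table must come out empty. The documents do not support that: it would happen only if the pembrolizumab field were used to attribute radiation toxicity, which nothing instructs. The reply does not supply the missing attribution, however. The natural reading of treatment-related is the one for which no field is described.

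A reader might also infer that the yes/no scale cannot serve local IRB reporting, where "this means an event should be considered probably or definitely related to the research procedures". That does not hold either. Section 8.2 offers this phrase as its meaning of reasonable possibility, the term used in Table 8's affirmative answer, so the protocol makes the link for pembrolizumab itself. For other procedures, nothing says the IRB decision is read from Table 8.

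Finally, Section 8.2 sends all grade 3 or higher events to the DSMC without an attribution test. That protects oversight of events that are recorded, but does not fill the endpoint table.

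**Conclusion.** The concern holds in this form: the plan calls for treatment-related toxicity of definitive therapy, and the causality assessment it describes does not record relationship to reirradiation or chemotherapy. The attribution is undefined, not zero. The gap covers the definitive phase for all 41 planned patients, and any later event judged due to radiation rather than pembrolizumab. The any-grade pneumonitis and esophagitis reports do not depend on attribution but share the recording-window problem.

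No count of lost events, and no confidence interval, can be attached: the documents give no rate of grade 3 or higher reirradiation toxicity, and the result depends on how analysts would fill the gap.

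The conclusion assumes that the case report form follows Table 8. If it already carries items for reirradiation and chemotherapy, what remains is to say so in the protocol, define the term and reconcile the recording window. This should be corrected. It does not affect the progression-free survival analysis.

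**What to change.** - In Table 8 and on the adverse event form, add a relationship item for proton reirradiation and one for concurrent chemotherapy beside the pembrolizumab item. Complete all three for every event, including those arising during pembrolizumab.
- In Sections 9.3.1 and 9.4, state that treatment-related for the definitive phase means related to reirradiation or to concurrent chemotherapy. State also in which table an event is counted when it arises during pembrolizumab but is attributed to definitive therapy.
- Reconcile Sections 3.1, 8.1.2.1 and 8.2 and the flow chart in Section 7.1 with the definitive-phase report, so that the events it needs are recorded from the start of reirradiation.

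The cost is two form fields, a short definition and the added event recording before pembrolizumab. Patient numbers do not change, and the flow chart already shows examinations during reirradiation at which events could be reviewed. Investigator attribution for patients already treated may not be reliably recoverable, so any retrospective assignment should be labelled as such.
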